2.8.1.1.2 Liver safety related AEs

Standardized MedDRA Queries (SMQs) are groupings of terms from one or more MedDRA SOCs that relate to a defined medical condition or area of interest. They are intended to aid in case identification.

SMQ Table: The number and percentage of patients experiencing adverse events categorized under the SMQ module drug-related hepatic disorders – comprehensive search (SMQ code 20000006, broad search) and its SMQ sub-modules will be reported.

SMQ-PT Table: The more detailed SMQ-PT table including the respective preferred term frequencies falling under the SMQ drug-related hepatic disorders – comprehensive search (SMQ code 20000006, broad search) and its SMQ sub-modules will be provided.

2.8.1.1.3 Other analyses

For the legal requirements of ClinicalTrials.gov and EudraCT, two required tables on non-serious treatment emergent adverse events with an incidence greater than 5% and on treatment emergent serious adverse events and SAE suspected to be related to study treatment will be provided by system organ class and preferred term on the safety set population.

If for a same patient, several consecutive AEs (irrespective of study treatment causality, seriousness and severity) occurred with the same SOC and PT:

- a single occurrence will be counted if there is ≤ 1 day gap between the end date of the preceding AE and the start date of the consecutive AE
- more than one occurrence will be counted if there is > 1 day gap between the end date of the preceding AE and the start date of the consecutive AE

For occurrence, the presence of at least one SAE / SAE suspected to be related to study treatment / non SAE has to be checked in a block e.g., among AE's in a ≤ 1 day gap block, if at least one SAE is occurring, then one occurrence is calculated for that SAE.

The number of deaths resulting from SAEs suspected to be related to study treatment and SAEs irrespective of study treatment relationship will be provided by SOC and PT.

2.8.2 Deaths

Death, if meaningful number of cases reported (i.e., 5 or more cases), will be summarized by providing the number and percentage of patients by treatment group. All deaths as recorded in the final database (i.e., up to database lock) will be included.

2.8.3 Laboratory data

Data summaries will be provided in SI units. The summary of laboratory evaluations will be presented for three groups of laboratory tests: Hematology, Chemistry and Urinalysis. On presenting summary statistics, laboratory data will be grouped and displayed in an alphabetical order within the Hematology and Chemistry groups and subgroups. Refer to [Section 5.3.1](#) for subgroup definitions.

Descriptive summary statistics (mean, median, standard deviation, Min and Max) of the change from baseline in the laboratory result to each study visit-window by treatment group will be presented. Change from baseline will only be summarized for patients with both baseline and post baseline values and will be calculated as:

$$\text{change from baseline} = \text{post baseline value} - \text{baseline value}$$

In addition, shift tables will be provided for all parameters to compare a patient's baseline laboratory evaluation relative to the post-baseline values. For the shift tables, the grade level based on CTC grade (as defined by CTCAE as listed in [Section 5.3.3](#)) will be used to evaluate whether a particular laboratory test value was Grade 0, 1, 2, 3, or 4 relative to whether or not

the baseline value was Grade 0, 1, 2, 3 or 4. These summaries will be presented by laboratory test and treatment group. Shift table will also be provided for urinalysis results to compare baseline to post-baseline extreme values (negative, +, 2+, 3+, or 4+).

The number and percentage of patients with new or worsening laboratory abnormalities based on CTC grade (as defined by CTCAE as listed in [Section 5.3.3](#)) in each visit-window and at any time post baseline will be presented. Patients with specific laboratory abnormalities (defined by CTC grade 3 and 4) will be listed.

Number of patients with newly occurring liver enzymes abnormalities will be summarized. Newly occurring liver enzymes abnormalities are defined in [Section 5.3.2](#).

Liver function tests will also be presented graphically as matrix plots of each of the parameters (ALT, AST, TBIL, ALP) maximum post-baseline/ULN normalized.

For the shift tables, abnormalities based on CTC grades tables and liver frequency distribution tables, all applicable post-baseline values will be checked against the respective criteria and the rules for handling multiple laboratory assessments within visit windows will not be applied.

For continuous variables databased as <lower limit, these will be imputed as being half of the lower limit.

All above summaries include only data up to and including safety cut off.

2.8.3.1 Liver events

Detailed information will be captured for patients with a reported liver event. For most studies patient listings may be appropriate because only a few liver events are expected, if any. However, respective tables with descriptive statistics may be provided if the number of liver events allows a meaningful interpretation, specifically if the number of liver events are greater than or equal to 10.

2.8.3.2 Renal events

Detailed information will be captured for patients with a reported renal event. The overall frequency and percentage of patients with confirmed renal events will be summarized by treatment group. Answers to “Event first identified through”, “Renal event associated signs and symptoms”, and “Any alternative diagnoses” (collected on diagnosis, follow up and overview pages) will also be summarized descriptively by treatment group. All data collected on the standard renal events CRF pages will be listed appropriately.

2.8.3.3 Serology at screening

Collected data of laboratory serology to determine patient’s eligibility includes parameters with respect to hepatitis and HIV viruses. Parameters with respect to hepatitis include 1) anti-hepatitis A virus IgM; 2) hepatitis B surface antigen and anti-hepatitis B core antigen IgM/IgG; 3) anti-hepatitis C virus antibody; 4) anti-hepatitis E virus IgM.

The result of each serology parameter is a categorical value. The number and percentage of patients with values in each of the categories will be provided by treatment group for all above mentioned parameters. Serology test should be performed once at screening. For patients with

multiple assessments, the latest result will be used in the summary. Additional serology data with numerical values may be collected but will not be reported.

2.8.3.4 Other special lab results

Other non-routine laboratory data include pregnancy test results, B-cell counts, teriflunomide plasma levels, total IgG, total IgM, [REDACTED]. All data will be listed appropriately.

The B-cell counts, total IgG, total IgM, neurofilaments [REDACTED] will be summarized using descriptive statistics by treatment group and visit-window.

In addition, number and percentage of patients with B-cells < the lower limit of normal (LLN) value (i.e., B-cell depleted) will be presented by treatment group and visit-window. Graphic presentation of B-cell counts distribution will also be provided by treatment group and visit-window. All B-cell summaries defined in this section will include data up to the end of the on-treatment period (i.e., last dose date + 30). This is to provide more accurate information about B-cell depletion because fast B-cell repletion is expected after study drug discontinuation and applying the safety cutoff (i.e., last dose date +100) would mix repletion and depletion to some degree.

Number and percentage of patients meeting the notable low level criteria in IgG or IgM at least once will be provided by treatment group. A notably low IgG level is defined as a level that is 20% below the LLN and a notably low IgM level is defined as a level 10% below the LLN.

2.8.4 ECG data

ECG data will be collected at baseline visit, EOT visit and EOS visit. Clinically significant findings from ECG evaluations will be reported as AEs and included in the analysis of AEs. ECG parameters include max heart rate, mean PR duration, mean QT duration, mean QRS duration, and QT corrected using Fridericia's correction formula (all as collected on the ECG CRF). Descriptive statistics of each ECG parameter will be provided by treatment group for baseline and for the 2 nominal visits (i.e., EOT and EOS visits).

The number and percentage of patients meeting the criteria defined in [Table 2-16](#) will be provided for each criterion by treatment group for baseline and for the 2 nominal visits.

Table 2-16 Criteria for relevant ECG absolute or change from baseline values

Absolute values criteria:	Changes from baseline criteria:
Heart rate: HR <40 or HR > 120 beats/min	QRS complex : increase > 25% compared to baseline
Pulse rate: PR <110 or PR >200 msec	QTcF > 500 msec and QTcF increase > 60 msec
QRS complex: < 70 msec or > 120 msec	
QTcF < 350 or > 450 msec (males)	
QTcF <360 or > 460 msec (females)	

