6.5.5 Electrocardiogram (ECG)

An ECG will be performed in this study as part of the eligibility assessment and at end of treatment/end of study. Additional unscheduled ECGs may be performed at Investigator's discretion if clinically indicated.

Single 12 lead ECGs are collected. The ECG should be recorded (after 10 minutes rest in the supine position to ensure a stable reading) according to the local site practice. Clinically significant ECG findings at Baseline must be discussed with the Sponsor before administration of study treatment.

The preferred sequence of cardiovascular data collection during study visits is ECG collection first, followed by vital signs, and blood sampling. The Fridericia QT correction formula (QTcF) should be used for clinical decisions.

The original ECGs on non-heat-sensitive paper / and a certified copy on non-heat sensitive paper), appropriately signed, must be collected and archived at the study site. Each ECG tracing must be labeled with study number, subject initials, subject number, date and time, and filed in the study site source documents.

Findings and clinically significant abnormalities must be recorded on the relevant section of the Medical history/Current medical conditions and AE CRF page as appropriate.

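### SAP Table 2-16 counts a QTcF increase above 60 msec only if QTcF also exceeds 500 msec, so the ECG table can under-report QTcF increases

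*SAP*

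**What the plan says.** SAP section 2.8.4 plans two ECG summaries.

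- **Descriptive statistics:** "Descriptive statistics of each ECG parameter will be provided by treatment group for baseline and for the 2 nominal visits". The two nominal visits are EOT and EOS.
- **Notable values:** the number and percentage of patients meeting the Table 2-16 criteria, which "will be provided for each criterion by treatment group for baseline and for the 2 nominal visits".

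The absolute column of Table 2-16 flags QTcF below 350 or above 450 msec in men, and below 360 or above 460 msec in women. The change column has two entries. One is "QRS complex : increase > 25% compared to baseline", a pure change. The other is "QTcF > 500 msec and QTcF increase > 60 msec", which joins an absolute limit to a change limit. There is no row for an increase above 60 msec alone, and none for QTcF above 500 msec alone.

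Protocol section 6.5.5 states: "The Fridericia QT correction formula (QTcF) should be used for clinical decisions". Protocol section 9.5.2 leaves the analysis of additional safety assessments, ECG among them, to the SAP.

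**The concern.** A row in a change-from-baseline column should count changes. This one counts a change only when the final value is also above 500 msec, so the increase it requires depends on where the patient started. A patient with a low or mid-range baseline can have a rise well beyond 60 msec and not be counted as having an increase. Some such patients appear nowhere among the QTcF rows.

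This matters for reading the safety report. A low or balanced count in that row could be taken to mean that few patients had QTcF increases above 60 msec, when the row does not measure that.

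**Working it through.** The plan states no figure to reproduce. The check applies the QTcF rows of Table 2-16 as logical rules to baseline and post-baseline values in whole msec.

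**Inputs (all from Table 2-16).** Absolute limits are 350-450 msec for men and 360-460 msec for women. The change row requires a post-baseline value above 500 msec and an increase above 60 msec.

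**1. Increase needed to meet the change row.** With baseline b, the post-baseline value must be at least 501 and the increase at least 61, so the required increase is max(61, 501 − b).

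| Baseline (msec) | Smallest increase counted (msec) |
|---|---|
| 380 | 121 |
| 400 | 101 |
| 420 | 81 |
| 440 or higher | 61 |

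A man going from 400 to 495 (+95) is counted only in the row for values above 450, not as an increase.

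**2. Increases that meet no QTcF row.** The increase is at least 61 and the final value does not exceed the upper absolute limit.

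- Men: b + 61 ≤ 450 gives b ≤ 389. For baselines 350-389, the largest unflagged rise is 450 − 350 = 100 msec.
- Women: b + 61 ≤ 460 gives b ≤ 399. For baselines 360-399, the largest unflagged rise is 460 − 360 = 100 msec.

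Examples are a man going from 370 to 445 (+75) and a woman going from 380 to 455 (+75).

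**3. Values above 500 msec with a smaller rise.** A final value of 501 with an increase of at most 60 needs a baseline of at least 441. A man going from 450 to 505 (+55) appears only in the above-450 row, together with someone at 451.

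**4. Illustration under an assumption.** The documents give no QTcF distribution. Assume a normal baseline with mean 395-415 and SD 15-20 msec, the same in both sexes. For a patient whose increase is d, the probability of meeting the joint row is 1 − Φ((500 − mean − d)/SD).

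| Increase d (msec) | Mean 395, SD 15 | Mean 415, SD 20 |
|---|---|---|
| 65 | 1 − Φ(2.67) = 0.4% | 1 − Φ(1.00) = 15.9% |
| 70 | 1 − Φ(2.33) = 1.0% | 1 − Φ(0.75) = 22.7% |
| 80 | 1 − Φ(1.67) = 4.8% | 1 − Φ(0.25) = 40.1% |

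The share exceeding no upper limit is Φ((limit − mean − d)/SD). At mean 405 and d of 65 to 70 msec:

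- Men (limit 450): from Φ(−1.67) = 4.8% (d = 70, SD 15) to Φ(−1.00) = 15.9% (d = 65, SD 20).
- Women (limit 460): from Φ(−1.00) = 15.9% (d = 70, SD 15) to Φ(−0.50) = 30.9% (d = 65, SD 20).

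These percentages are conditional on a patient having such an increase. They do not say how many patients would.

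**5. Other planned outputs.** SAP sections 2.8.3 (laboratory) and 2.8.5 (vital signs) specify change-from-baseline summaries. Section 2.8.4 specifies none for ECG beyond Table 2-16. Section 5.3.2 lists liver thresholds singly (for example ALT above 3x ULN, TBIL above 2x ULN) and then jointly. Table 2-16 gives the 500 and 60 msec limits only in joint form.

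**The case against.** **Other outputs show outliers.** SAP section 2.1 includes the minimum and maximum in continuous summaries, so the highest QTcF in each arm is tabulated at each visit, and a shift in the mean would be visible. Clinically significant ECG findings are reported as adverse events and analysed by arm, and all data are listed. This stands. A reader might infer that Table 2-16 is the only view of QTcF outliers, but the documents do not support that. None of these outputs, however, counts QTcF increases by arm: a maximum is a single value, listings are not counts, and adverse event reporting rests on the investigator's judgement.

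**The change row need not be nearly empty.** A reader might also infer that it would be almost blank whatever the drug does. That does not follow. Under the assumed distribution it catches up to about 23% of +70 msec increases and up to about 40% at +80 msec. Most men with +65 to +70 msec would also be flagged by the above-450 row, though not as an increase.

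**The word joining the limits may be a loose list.** Two criteria may have been intended. But they sit in one cell, counts are given per criterion, and the absolute rows use 'or' for alternatives, so a programmer would code a conjunction. On either reading the cell needs rewording.

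**The setting is low-stakes.** ECGs are single 12-lead tracings at screening or baseline, EOT and EOS. The risks listed in Protocol section 3.6 include no QT effect, familial long QT is excluded, and no hypothesis is attached to the table. This supports a minor grading; it does not make the row count what its column heading says.

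**Conclusion.** The point holds as a minor weakness in a descriptive safety table. On the literal reading, QTcF increases above 60 msec ending at or below 500 msec are not counted as increases, and rises of up to 100 msec from baselines within the table's limits can meet no QTcF row. These results follow from the printed thresholds and need no distributional assumption. The capture percentages do need one and are illustrative only.

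The documents do not show that a QTcF effect would go unseen, that any patient in this trial is affected, or that either drug prolongs QTcF. What they show is that the planned output cannot supply a by-arm count of QTcF increases.

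**What to change.** In Table 2-16, replace the joint QTcF entry with two criteria reported separately: QTcF above 500 msec in the absolute column, and QTcF increase above 60 msec from baseline in the change column. The joint criterion may stay as a third row. This follows the single-then-joint pattern of SAP section 5.3.2. The cost is a wording change and two extra rows from ECG data already collected.

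Two clerical corrections can be made at the same time. The row "Pulse rate: PR <110 or PR >200 msec" carries PR-interval limits in msec and should be labelled as PR interval. Change criteria should be tabulated only at EOT and EOS, since change at baseline is zero by definition.

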2.8.5 Vital signs

Vital sign measurements include sitting systolic and diastolic blood pressures, sitting pulse, body temperature, height and body weight.

Three sitting measurements of blood pressure (SBP and DBP) and pulse will be taken at each vital sign assessment.

For post-baseline assessments, the blood pressure and pulse values will be the average of the non-missing values of the 3 measurements. If more than one blood pressure/pulse assessment (scheduled or unscheduled) exists in a particular visit-window (as defined in [Section 2.1.2.1](#)), derivation should follow the rules as defined in [Section 2.1.2.3](#). Derivation of baselines for blood pressure and pulse are provided in [Section 2.1.1](#).

Height will be collected at screening visit only and will be summarized in the baseline characteristic summary only.

Analyses of vital sign measurements (excluding data collected on Day 1, Day 7, Day 14 and Month 1 protocol scheduled visit) using descriptive summary statistics (mean, median, standard deviation, min, max) for the change from baseline for each post-baseline visit-window will be performed. These descriptive summaries will be presented by vital sign parameter and treatment group. Change from baseline will only be summarized for patients with both baseline and post-baseline values and will be calculated as:

$$\text{change from baseline} = \text{post-baseline value} - \text{baseline value}$$

The number and percentage of patients with clinically notable vital signs will be presented. For clinical notable vital signs values, refer to [Section 5.4](#).

For vital signs data collected on Day 1, Day 7, Day 14 and Month 1 protocol scheduled visit, pre and post-injection vital signs data including temperature, pulse rate and blood pressure are collected. Change from pre-injection to post-injection in these 3 parameters will be summarized by nominal visit.

All above summaries include only data up to and including safety cut off.

2.8.6 Suicidality evaluations

The Columbia Suicide Severity Rating Scale (C-SSRS) questionnaire will be administered electronically (eC-SSRS), via an interactive voice response (IVR) system. However, as per internal Novartis guidelines, a CRF page ‘Supplemental Data for Suicidal Ideation and Behavior Categories’ is also used as an unplanned/unscheduled visit for those cases when the subject did not conduct the phone interview because, e.g. the subject was hospitalized and unable to conduct the interview or the subject refused to conduct the interview/withdrew from the study and external information on suicidal ideation and behavior (SIB) is required. In such cases, SIB information will still be collected from external parties (spouse, caregiver, nurse, investigator, etc.) through means of this CRF page. Further, for deaths due to suicide, the site should fill out the Supplemental Data CRF (“completed suicide” tickbox) to ensure accurate reporting of such cases. When reporting the SIB data, data from both sources (IVR eC-SSRS and Supplemental CRF) will be used in a pooled manner and no distinction will be made between the two.

Table 2-17 Standard SIB events as categorized by C-SSRS

Category number	C-SSRS category
Suicidal Ideation	
1	Wish to be dead
2	Non-specific active suicidal thoughts
3	Active suicidal ideation with any methods (not plan) without intent to act
4	Active suicidal ideation with some intent to act, without specific plan
5	Active suicidal ideation with specific plan and intent
Suicidal behavior	
6	Preparatory acts or behavior
7	Aborted attempt
8	Interrupted attempt
9	Actual attempt
10	Completed suicide
Self-injurious behavior, without suicidal intent	
11	Non-suicidal self-injurious behavior

Definition of ‘all prior history’ and ‘recent history’

SIB will be collected once before randomization, either at screening or at baseline visits. SIB assessments obtained before the first dose of study drug will be defined by two components: *all prior history and recent history*.

All prior history will be defined as the SIB results obtained from the *lifetime* assessment, and *recent history* will be defined as the SIB results obtained from the *pre-defined period* (i.e., *past 6 months or 24 months*) assessment of the screening or baseline visit. In case multiple assessments collected before first dose of study drug, results should be derived as the worst case value per the reporting timeframe. Worst case is defined by an answer ‘yes’ to the SIB category.

Data summaries

SIB data will be summarized for the Safety set. The number and percentage of subjects with suicidal ideation, suicidal behavior and self-injurious behavior without suicidal intent will be presented by analysis-period (recent history, all prior history and any time post-baseline) and treatment group. The following 14 events will be included in the summary table:

- Each of the 11 categories listed in [Table 2-17](#), separately
- Any suicidal ideation or behavior (a ‘yes’ answer to at least one of the 10 suicidal ideation and behavior questions in analysis-period of interest)
- Any suicidal ideation (answered ‘yes’ to at least one of the 5 suicidal ideation questions in analysis-period of interest)
- Any suicidal behavior (answered ‘yes’ to at least one of the 5 suicidal behavior questions in analysis-period of interest)

In addition, the number and percentage of subjects with the following post-baseline events will be presented ([Nilsson et al. 2013](#)):

Note: in these definitions, a category of 0 is assigned to a subject without suicidal ideation (i.e. a 'no' answer to all suicidal ideation categories)

- Worsening suicidal ideation compared to recent history: An increase in the maximum suicidal ideation category at any time post-baseline from the maximum suicidal ideation category during pre-treatment recent history.
- Worsening serious suicidal ideation compared to recent history: An increase in the maximum suicidal ideation category to 4 or 5 at any time post-baseline from not having serious suicidal ideation (categories of 0-3) during pre-treatment recent history.
- Emergence of serious suicidal ideation compared to recent history: A maximum suicidal ideation category of 4 or 5 at any time post-baseline from no suicidal ideation (category 0) during pre-treatment recent history.
- Improvement in suicidal ideation at last on-treatment measurement compared to recent history: A decrease in suicidal ideation score at last on-treatment measurement from pre-treatment recent history.
- Emergence of suicidal behavior compared to all prior history: The occurrence of suicidal behavior (Categories 6-10) at any time post-baseline from not having suicidal behavior (Categories 6-10) prior to treatment (includes "lifetime" and any other assessments prior to treatment taken prior to treatment).

For those analyses, each subject can only be counted once for each event. However, a subject can be counted in several different events.

Suicidal ideation and behavior data will be listed. Detailed answers to C-SSRS items will be listed separately for subjects with any suicidal ideation at any time post-baseline (i.e. a 'yes' answer to at least one of the five suicidal ideation questions at any time post-baseline) and for a subject with any suicidal behavior at any time post-baseline (i.e. a 'yes' answer to at least one of the five suicidal behavior questions at any time post-baseline).

